11.7. Appendix 7: Reporting Standards for Missing Data

11.7.1. Premature Withdrawals

Element	Reporting Detail
General	
 Participant study completion (i.e. as specified in the protocol) was defined as he/she has completed all phases of the study including the safety follow-up telephone contact or clinic visit. Withdrawn participants were not replaced in the study. All available data from participants who were withdrawn from the study will be listed and all available planned data will be included in summary tables and figures, unless otherwise specified. Withdrawal visits will not be slotted and not be summarized as Withdrawal visit.

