8.5. Clinical Laboratory Analyses

Laboratory evaluations including the analyses of Chemistry laboratory tests, Hematology laboratory tests, Urinalysis, and liver function tests will be based on GSK Core Data Standards. The details of the planned displays are in [Appendix 11: List of Data Displays](#).

Clinical laboratory will be measured at visit 1 (screening visit), 4 (Week 12), 5 (Week 24), 7 (Week 52) or EW. and will be summarized by dose group.

Raw value and change from baseline for laboratory data will be summarized by dose group and total for each visit.

Shifts from baseline relative to the normal range will be also summarized by dose group and total for each visit.

The number of participants with worst case chemistry or hematology will be summarized by test and category. The categories for normal range are: To Low, To Normal or No Change, To High. The categorization is determined by comparing the baseline category to the worst case post-baseline category. The determination of the worst case post-baseline takes into account both planned and unscheduled assessments. The percentages are based on the number of participants in the dose group with data for the test post-baseline. Participants with missing baseline value are to be assumed to have normal/within range baseline value. Note that if a subject has both a decrease ‘To Low’ and an increase ‘To High’, then the subject is counted in both the ‘To Low’ and ‘To High’ categories, so the percentages may not add to 100%.

The number of participants with worst case protein (category: NEG, TRA, 1+, 2+, 3+) or occult blood (category: NEG, TRA, 1+, 2+, 3+) urinalysis results will be summarized by test and category. The categories for worst case are: No Change/Decresed, Any Increase, Increase to TRA, Increase to 1+, Increase to 2+, Increase to 3+. The categorization is determined by comparing the baseline category to the worst case post-baseline category. The determination of the worst case post-baseline takes into account both planned and unscheduled assessments. The percentages are based on the number of participants in the dose group with data for the test post-baseline. Participants with missing baseline value are to be assumed to have normal/within range baseline value.

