8.6.1. Vital signs

Vital signs will be measured at every clinical visit and will be summarized by dose group and total.

Raw value and change from baseline for Vital signs will be summarized by dose group and total for each visit.

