8.6.2. ECG

12-lead ECGs are measured at Visit 1, 3, 5 and 7, and at Early Withdrawal visit. The ECG measurements of interest are QTc (F), heart rate, and PR interval. All ECG data present in the database will be considered valid and will be reported (even if the ECG had a technical error).

Raw value and change from baseline for ECG values will be summarized by dose group and total for each visit.

A ‘maximum post-baseline’ QTc (F), PR interval, and heart rate value will be derived as the maximum on-treatment value recorded at any scheduled, unscheduled, or EW visit after the start of study treatment.

QTc (F) values (including ‘maximum post-baseline’) will be categorized as follows: $\leq 450\text{msec}$, >450 to $\leq 480\text{msec}$, >480 to $\leq 500\text{msec}$, >500 to $\leq 530\text{msec}$ and $>530\text{msec}$. Change from baseline QTc (F) values (including change to ‘maximum post baseline’) will be categorized as follows: $\leq -60\text{msec}$, >-60 to $\leq -30\text{msec}$, >-30 to $\leq 0\text{msec}$, >0 to $\leq 30\text{msec}$, >30 to $\leq 60\text{msec}$, and $>60\text{msec}$.

An ‘any time post-baseline’ ECG interpretation will be derived as the worst on-treatment interpretation recorded at a scheduled, unscheduled, or EW visit after the start of study treatment. The worst case post-baseline is defined as:

- ‘Abnormal’ if any assessment during treatment period is evaluated as ‘Abnormal’
- ‘Unable to evaluate’ if all assessments during treatment period are ‘Unable to evaluate’
- ‘Normal’ if any assessment during treatment period is evaluated as ‘Normal’ and there are no assessments evaluated as ‘Abnormal’ during treatment period

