11.3. Appendix 3: Assessment Windows

11.3.1. Clinical visits

Clinic visits are scheduled to take place as specified in the protocol. Measurements outside visit windows will not be excluded from analyses on any population.

For all clinic visits, nominal visits will be used for reporting.

All unscheduled visits will be included in listings.

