11.5.2. Reporting Standards

General

 The current GSK Integrated Data Standards Library (IDSL) will be applied for reporting, unless otherwise stated (IDSL Standards Location: https://spope.gsk.com/sites/IDSLLibrary/SitePages/Home.aspx): 
 4.03 to 4.23: General Principles 5.01 to 5.08: Principles Related to Data Listings 6.01 to 6.11: Principles Related to Summary Tables 7.01 to 7.13: Principles Related to Graphics
Formats

 GSK IDSL Statistical Principles (5.03 & 6.06.3) for decimal places (DP's) will be adopted for reporting of data based on the raw data collected, unless otherwise stated. Numeric data will be reported at the precision collected on the eCRF. The reported precision from non eCRF sources will follow the IDSL statistical principles but may be adjusted to a clinically interpretable number of DP's.
Planned and Actual Time

 Reporting for tables, figures and formal statistical analyses: 
 Planned time relative to dosing will be used in figures, summaries, statistical analyses and calculation of any derived parameters, unless otherwise stated. The impact of any major deviation from the planned assessment times and/or scheduled visit days on the analyses and interpretation of the results will be assessed as appropriate. Reporting for Data Listings: 
 Planned and actual time relative to study drug dosing will be shown in listings (Refer to IDSL Statistical Principle 5.05.1). Unscheduled or unplanned readings will be presented within the subject's listings.
Unscheduled Visits

 Unscheduled visits will not be included in summary tables and/or figures except as part of a 'worst case post-baseline' assessment.

• All unscheduled visits will be included in listings.	
Descriptive Summary Statistics	
Continuous Data	Refer to IDSL Statistical Principle 6.06.1
Categorical Data	N, n, frequency, %
Graphical Displays	
• Refer to IDSL Statistical Principals 7.01 to 7.13.	

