11.8. Appendix 8: Values of Potential Clinical Importance

This is not applicable to this study.

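### Blood pressure and pulse readings from early-withdrawal visits enter no row that the SAP specifies for the vital-signs tables, although the ECG maxima do include such visits

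*SAP*

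**What the plan says.** - Protocol section 4 names blood pressure and pulse as a secondary safety endpoint. Protocol Table 1 schedules vital signs at every clinic visit from screening to Week 52 and at the EW visit.
- SAP 8.6.1 gives the whole vital-signs analysis: "Raw value and change from baseline for Vital signs will be summarized by dose group and total for each visit". SAP 11.3.1 fixes how visits are labelled: "For all clinic visits, nominal visits will be used for reporting".
- SAP 11.7.1 first sets a general rule for withdrawn participants, that "all available planned data will be included in summary tables and figures, unless otherwise specified". It then makes an exception: "Withdrawal visits will not be slotted and not be summarized as Withdrawal visit".
- SAP 11.5.2 says of unscheduled visits: "Unscheduled visits will not be included in summary tables and/or figures except as part of a" worst-case post-baseline assessment. The appendix on values of potential clinical importance (SAP 11.8) reads: "This is not applicable to this study".
- SAP 8.6.2 defines maximum post-baseline QTcF, PR and heart rate as the largest value "recorded at any scheduled, unscheduled, or EW visit after the start of study treatment". For laboratory categories, SAP 8.5 says: "The determination of the worst case post-baseline takes into account both planned and unscheduled assessments".

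**The concern.** For a participant who stops early, the EW reading is normally the last one taken in the treatment period. The treatment-period definition in SAP 11.4.1 runs through the EW date, and Protocol 8.1.3 requires anyone who discontinues treatment to leave the study. The readings left out of the tables are therefore not a random subset. They belong only to people who stopped, at the time they stopped.

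Protocol 3.3.1 lists vital-sign assessment among the mitigations for cardiovascular effects of UMEC and VI. The SAP already lets EW values into the ECG maxima and gives no reason for handling blood pressure differently. The interim tables, prepared for the Japanese submission, follow the same rules, although SAP 3.1 places data up to the date of a pre-Week 24 withdrawal inside the interim cut-off.

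**Working it through.** **Tracing one EW blood pressure reading through the SAP**

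1. *Collected?* Yes, by the EW column of Protocol Table 1.
2. *In the treatment period?* Yes, by SAP 11.4.1.
3. *In a by-visit row?* No. Rows follow nominal visits, and the withdrawal visit is neither mapped to a scheduled visit nor given its own row. The general rule on planned data yields to this specific one.
4. *In a maximum, minimum or worst-case row?* SAP 8.6.1 defines none.
5. *In a table of clinically important values?* None is planned (SAP 11.8).
6. *Elsewhere?* In the vital-signs listings only: Listing 30 (interim) and Listing 74 (final). Both carry a programming note limiting them to clinical pharmacology studies, yet both are assigned as deliverables. I take the assignment as governing.

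The rows specified for the four vital-signs tables (2.26, 2.27, 12.45, 12.46) therefore take no EW readings. An unscheduled post-baseline reading would fare the same, because its only way in is a worst-case assessment that vital signs lack. The schedule plans no such readings.

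**How many participants**

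Inputs are from Protocol 10.1: 110 enrolled, 100 completers, approximately 10% dropout.

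- The plan's own figure: 110 × (1 − 0.10) = 99 completers, in line with the stated 100.
- Expected early withdrawals: 110 − 100 = 10 (10/110 = 9.1%), or 110 × 0.10 = 11.
- If dropout differed (my assumed range): 110 × 0.05 = 5.5 and 110 × 0.20 = 22, so about 6 to 22.

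**How late the omitted reading can be**

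Inputs are the nominal vital-signs days in Protocol Table 1.

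| Interval | Days | Gap |
|---|---|---|
| Week 0 to 4 | 1 to 29 | 28 |
| Week 4 to 12 | 29 to 85 | 56 |
| Week 12 to 24 | 85 to 169 | 84 |
| Week 24 to 36 | 169 to 253 | 84 |
| Week 36 to 52 | 253 to 365 | 112 |

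With no missed visit, the EW reading can be roughly 84 days later than the last tabulated one if withdrawal comes before Week 36, and 112 days later after Week 36. Using the −5/+2 day visit windows (previous visit 5 days early, next visit 2 days late) gives 84 + 7 = 91 and 112 + 7 = 119. A participant who leaves before Week 4 has no post-baseline blood pressure or pulse in the by-visit rows.

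**The case against.** The strongest reply is that this is a stated choice in a descriptive study with no hypotheses. All data from withdrawn participants are listed, and about 10 withdrawers can be reviewed in a listing. That stands, and it keeps the point small.

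Other replies also narrow it:

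- *Pulse.* ECG is recorded at EW and its maximum heart rate includes EW, so a high rate at withdrawal already has a numeric derivation. What remains is blood pressure and low pulse.
- *Adverse events.* Clinically significant vital-sign changes are reportable as AEs (Protocol Appendix 3). Hypertension is a special-interest subgroup (SAP 8.3), AEs leading to withdrawal have their own tables, and a hypertension patient profile is planned. These displays depend on investigator reporting and do not summarise blood pressure values.
- *Basis for the contrast.* QTc has stopping thresholds and laboratory tests have reference ranges, whereas the documents give none for blood pressure. That may explain why no categories were built, but a maximum or last value needs no threshold. The laboratory wording does not name EW visits, so ECG is the cleaner comparison.
- *Unscheduled readings.* Protocol 9.4.2 asks for a single set of values, and the repeat-sampling provision in Protocol section 9 concerns blood samples. There may be none.
- *Unseen shell.* SAP 8.6 defers to sponsor standards, and the tables use shell VS1, which is not in the documents. It might carry an extra row.

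A reader might infer that SAP 11.7.1 contradicts itself, or that withdrawers' vital signs are lost. Neither follows. The general rule allows exceptions and the next statement is one. Scheduled visits that a withdrawer attended still count, and the EW values are listed.

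**Conclusion.** The point holds in a limited form, with medium confidence. By the rules written in the SAP, EW blood pressure and pulse reach no specified row of the vital-signs tables, while EW values do enter the ECG maxima. The expected size is about 10 to 11 of 110 participants. This assumes that dropout is as planned and that every withdrawer attends an EW visit; it is an expectation, not a ceiling. The 84- and 112-day figures assume no missed visits. The schedule sets no window for the EW visit, so they are not strict limits.

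It would go too far to say that these readings can appear in no numeric table at all, since the VS1 shell cannot be checked. It would also go too far to say that a blood pressure signal would be hidden: the effect on the results cannot be derived. No primary analysis or decision rule changes. This is an inexpensive improvement to the display of a secondary safety endpoint.

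**What to change.** - In SAP 8.6.1, define maximum, minimum and last post-baseline systolic pressure, diastolic pressure and pulse, as value and change from baseline. Use all scheduled, unscheduled and EW readings after the first dose and through the date of Visit 7/EOT or EW, which is the treatment period of SAP 11.4.1. Do not use the treatment-emergent rule in SAP 11.4.2. It ends at the treatment stop date and would exclude an EW reading taken after that date.
- Add these rows to Tables 12.45/12.46 and, limited to the interim cut-off, to Tables 2.26/2.27. The last-value row is needed because a maximum or minimum shows the EW reading only when it is that participant's extreme.
- In SAP 11.7.1, state that EW values are not slotted but do enter these rows. Leave the by-visit rows unchanged.
- If VS1 already contains such a row, say so in 8.6.1 and confirm that EW readings count.

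The cost is SAP wording and a little programming on data already collected, with no protocol amendment. Participants with more readings have more chances of an extreme value, which a table footnote should mention. The vital-signs results may look slightly less favourable.

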11.7.2. Handling of Missing Data

Element	Reporting Detail
General	
 Missing data occurs when any requested data is not provided, leading to blank fields on the collection instrument: 
 These data will be indicated by the use of a "blank" in participant listing displays. Unless all data for a specific visit are missing in which case the data is excluded from the table. Answers such as "Not applicable" and "Not evaluable" are not considered to be missing data and should be displayed as such.
Outliers	
 Any participants excluded from the summaries and/or statistical analyses will be documented along with the reason for exclusion in the clinical study report.

11.7.2.1. Handling of Missing and Partial Dates

Element	Reporting Detail
General	
 Partial dates will be displayed as captured in participant listing displays.
Adverse Events	
 The eCRF does not allow for the possibility of partial dates (i.e., only month and year) to be recorded for AE start and end dates; that is, the day of the month may be missing. Completely missing start or end dates will remain missing, with no imputation applied. Consequently, time to onset and duration of such events will be missing.
Concomitant Medications/ Medical History	
 Partial dates for any concomitant medications recorded in the CRF will be imputed using the following convention: 
 If the partial date is a start date, a '01' will be used for the day and 'Jan' will be used for the month If the partial date is a stop date, a '28/29/30/31' will be used for the day (dependent on the month and year) and 'Dec' will be used for the month. The recorded partial date will be displayed in listings.

11.8. Appendix 8: Values of Potential Clinical Importance

This is not applicable to this study.

11.9. Appendix 9: Implementation and mitigation strategy of Statistical Output Review (SOR)

This appendix describes what Japan S&P team will do as SOR and its mitigation strategy to maintain integrity of study.

Background:

In this study, SOR will be planned before release of randomization code from RandAll. The purpose of SOR is to make sure programming was in place and to check formatting of outputs, NOT to review the data itself. According to GSK SOP_57860, a dry run on a single arm open label study is the same as an interim analysis, so unless it's detailed in the protocol, that should not be done. Therefore, the mitigation strategy should be described in this RAP.

What Japan S&P team will do:

- Lead statistician and lead programmer will make sure programming was in place and to check formatting of outputs.
- Additional reviewers in Japan S&P will help to make sure programming works well and check formatting of outputs.

Mitigation strategy:

- Japan S&P team will NOT share any results with outside of Japan S&P team at the timing of SOR or prior to interim SAC.
- HARP environment will also be restricted to Japan S&P team and programmers.

11.10. Appendix 10: Abbreviations & Trade Marks

11.10.1. Abbreviations

Abbreviation	Description
ADaM	Analysis Data Model
AE	Adverse Event
AIC	Akaike's Information Criteria
A&R	Analysis and Reporting
CDISC	Clinical Data Interchange Standards Consortium
CI	Confidence Interval
CS	Clinical Statistics
CSR	Clinical Study Report
CTR	Clinical Trial Register
DBF	Database Freeze
DBR	Database Release
DOB	Date of Birth
DP	Decimal Places
eCRF	Electronic Case Record Form
EMA	European Medicines Agency
FDA	Food and Drug Administration
FDAAA	Food and Drug Administration Clinical Results Disclosure Requirements
GSK	GlaxoSmithKline
IA	Interim Analysis
ICH	International Conference on Harmonization
IDMC	Independent Data Monitoring Committee
IDSL	Integrated Data Standards Library
IMMS	International Modules Management System
IP	Investigational Product
ITT	Intent-To-Treat
MACE	Major Adverse Cardiac Event
MMRM	Mixed Model Repeated Measures
PCI	Potential Clinical Importance
PDMP	Protocol Deviation Management Plan
PLS	Plain Language Summary
PP	Per Protocol
QC	Quality Control
QTcF	Frederica's QT Interval Corrected for Heart Rate
QTcB	Bazett's QT Interval Corrected for Heart Rate
RAP	Reporting & Analysis Plan
RAMOS	Randomization & Medication Ordering System
SAC	Statistical Analysis Complete
SDSP	Study Data Standardization Plan
SDTM	Study Data Tabulation Model
SOP	Standard Operation Procedure

Abbreviation	Description
TA	Therapeutic Area
TFL	Tables, Figures & Listings

11.10.2. Trademarks

Trademarks of the GlaxoSmithKline Group of Companies	Trademarks not owned by the GlaxoSmithKline Group of Companies
ELLIPTA	SAS

11.11. Appendix 11: List of Data Displays

11.11.1. Data Display Numbering

The following numbering will be applied for RAP generated displays:

At interim analysis:

Section	Tables	Figures
Study Population	1.1 to 1.n	NA
Safety	2.1 to 2.n	NA
Other	3.1 to 3.n	NA
Section	Listings	
ICH Listings	1 to x	
Other Listings	y to z	

At final analysis:

Section	Tables	Figures
Study Population	11.1 to 1.n	NA
Safety	12.1 to 2.n	NA
Other	13.1 to 3.n	NA
Section	Listings	
ICH Listings	44 to x	
Other Listings	y to z	

11.11.2. Deliverables

Delivery [Priority] ^[1]	Description
IA [X]	Interim Analysis Statistical Analysis Complete
SAC [X]	Final Statistical Analysis Complete

NOTES:

1. Indicates priority (i.e. order) in which displays will be generated for the reporting effort

CONFIDENTIAL

207236

11.11.3. Study Population Tables (interim)

Study Population Tables					
No.	Population	IDSL / Example Shell	Title	Programming Notes	Deliverable [Priority]
Subject Disposition					
1.1.	ITT	ES1	Summary of Subject Disposition (Interim)	ICH E3, FDAAA, EudraCT	IA [1]
1.2.	ITT	SD1	Summary of Treatment Status (Interim)	ICH E3	IA [1]
1.3.	Enrolled	ES4	Summary of Participant Disposition at Each Study Epoch (Interim)	ICH E3	IA [1]
1.4.	Screened	ES6	Summary of Screening Status and Reasons for Screen Failure and Run-in Failure (Interim)	Journal Requirements	IA [1]
1.5.	Enrolled	NS1	Summary of Number of Participant by Country and Site ID (Interim)	EudraCT/Clinical Operations	IA [1]
Protocol Deviation					
1.6.	ITT	DV1	Summary of Important Protocol Deviations (Interim)	ICH E3	IA [1]
Population Analysed					
1.7.	All Subjects	SP1	Summary of Study Populations (Interim)	IDSL	IA [1]
Demographic and Baseline Characteristics					
1.8.	ITT	DM1	Summary of Demographic Characteristics (Interim)	ICH E3, FDAAA, EudraCT	IA [1]
1.9.	Enrolled	DM11	Summary of Age Ranges (Interim)	EudraCT	IA [1]
1.10.	ITT	DM5	Summary of Race and Racial Combinations (Interim)	ICH E3, FDA, FDAAA, EudraCT	IA [1]
1.11.	ITT	Study Specific	Summary of Disease Duration (Interim)		IA [1]
1.12.	ITT	Study Specific	Summary of Asthma Medical History Questionnaire (Interim)		IA [1]
1.13.	ITT	Study Specific	Summary of Exacerbation History (Interim)		IA [1]
1.14.	ITT	SU1 (subset)	Summary of Smoking Status (Interim)		IA [1]

CONFIDENTIAL

207236

Study Population Tables					
No.	Population	IDSL / Example Shell	Title	Programming Notes	Deliverable [Priority]
1.15.	ITT	Study Specific	Summary of Cardiovascular History / Risk Factors (Interim)		IA [1]
1.16.	ITT	FH1	Summary of Family History of Cardiovascular Risk Factors (Interim)		IA [1]
1.17.	ITT	Study Specific	Summary of ACQ-6 score at Screening (Interim)		IA [1]
1.18.	ITT	Study Specific	Summary of Clinic Spirometry at Baseline (Interim)		IA [1]
Prior and Concomitant Medications					
1.19.	ITT	MH4	Summary of Current Medical Conditions (Interim)	ICH E3	IA [1]
1.20.	ITT	MH4	Summary of Past Medical Conditions (Interim)	ICH E3	IA [1]
1.21.	ITT	CM1	Summary of Asthma Concomitant Medications Before Study Treatment (Interim)		IA [1]
1.22.	ITT	CM1	Summary of Asthma Concomitant Medications During the Treatment Period (Interim)		IA [1]
1.23.	ITT	CM1	Summary of Non-Asthma Concomitant Medications During the Treatment Period (Interim)		IA [1]
Exposure and Treatment Compliance					
1.24.	ITT	Study Specific	Summary of Treatment Compliance (Interim)		IA [1]

CONFIDENTIAL

207236

11.11.4. Study Population Tables (final)

Study Population Tables					
No.	Population	IDSL / Example Shell	Title	Programming Notes	Deliverable [Priority]
Subject Disposition					
11.1.	ITT	ES1	Summary of Subject Disposition	ICH E3, FDAAA, EudraCT	SAC [1]
11.2.	ITT	SD1	Summary of Treatment Status	ICH E3	SAC [1]
11.3.	Enrolled	ES4	Summary of Participant Disposition at Each Study Epoch	ICH E3	SAC [1]
Protocol Deviation					
11.4.	ITT	DV1	Summary of Important Protocol Deviations	ICH E3	SAC [1]
Population Analysed					
11.5.	All Subjects	SP1	Summary of Study Populations	IDSL	SAC [1]
Demographic and Baseline Characteristics					
11.6.	ITT	DM1	Summary of Demographic Characteristics	ICH E3, FDAAA, EudraCT	SAC [1]
11.7.	Enrolled	DM11	Summary of Age Ranges	EudraCT	SAC [1]
11.8.	ITT	DM5	Summary of Race and Racial Combinations	ICH E3, FDA, FDAAA, EudraCT	SAC [1]
11.9.	ITT	Study Specific	Summary of Disease Duration		SAC [1]
11.10.	ITT	Study Specific	Summary of Asthma Medical History Questionnaire		SAC [1]
11.11.	ITT	Study Specific	Summary of Exacerbation History		SAC [1]
11.12.	ITT	SU1 (subset)	Summary of Smoking Status		SAC [1]
11.13.	ITT	Study Specific	Summary of Cardiovascular History / Risk Factors		SAC [1]
11.14.	ITT	FH1	Summary of Family History of Cardiovascular Risk Factors		SAC [1]
11.15.	ITT	Study Specific	Summary of ACQ-6 score at Screening		SAC [1]
11.16.	ITT	Study Specific	Summary of Clinic Spirometry at Baseline		IA [1]

CONFIDENTIAL

207236

Study Population Tables					
No.	Population	IDSL / Example Shell	Title	Programming Notes	Deliverable [Priority]
Prior and Concomitant Medications					
11.17.	ITT	MH4	Summary of Current Medical Conditions	ICH E3	SAC [1]
11.18.	ITT	CM1	Summary of Asthma Concomitant Medications During the Treatment Period		SAC [1]
11.19.	ITT	CM1	Summary of Asthma Concomitant Medications During the Follow-Up Period		SAC [1]
11.20.	ITT	CM1	Summary of Non-Asthma Concomitant Medications During the Treatment Period		SAC [1]
11.21.	ITT	CM1	Summary of Non-Asthma Concomitant Medications During the Follow-Up Period		SAC [1]
Exposure and Treatment Compliance					
11.22.	ITT	Study Specific	Summary of Treatment Compliance		SAC [1]

CONFIDENTIAL

207236

